11.1 TOXICITIES/SIDE EFFECTS

11.1 Debio 1347

Expected side effects include:

- **Constitutional:** asthenia, fatigue, decreased appetite
- **Musculoskeletal:** myalgia, back pain
- **Neurologic:** dizziness
- **Cardiovascular:** hypertension, decline in LVEF, QTc prolongation
- **ENT:** blurry vision, diplopia, dry eyes
- **Respiratory:** dyspnea, cough
- **Dermatologic:** maculo papular rash, nail changes, alopecia, hand foot syndrome, dry skin

- **Gastrointestinal:** elevations in AST/ALT/Alk Phos/bilirubin/amylasemia, nausea/vomiting, constipation, diarrhea, abdominal pain, dry mouth, dysgeusia, stomatitis
- **Renal/Electrolyte abnormalities:** hyperphosphatemia, increased creatinine, hypomagnesemia, hypokalemia

Please refer to Section 3.3.4 and the Investigator's Drug Brochure for more information.

11.2 Fulvestrant

The most common adverse reactions occurring in ≥5% of patients receiving 500 mg fulvestrant were: injection site pain, nausea, bone pain, arthralgia, headache, back pain, fatigue, pain in extremity, hot flash, vomiting, anorexia, asthenia, musculoskeletal pain, cough, dyspnea, and constipation.

Increased hepatic enzymes (ALT, AST, ALP) occurred in >15% of FASLODEX users and were not dose-dependent.

Because Fulvestrant is administered intramuscularly, it should be given with caution in patients with bleeding diathesis, thrombocytopenia, or anticoagulant use. For further details regarding the safety profile of fulvestrant, refer to the fulvestrant package insert.

12.0 CRITERIA FOR THERAPEUTIC RESPONSE/OUTCOME ASSESSMENT

Tumor response is based on the RECIST v.1.1. A copy of the full article is provided as Appendix B. Key elements of the criteria are summarized below.

12.1 Measurability of Tumor at Baseline

RECIST v.1.1 provides the following definitions for designating the tumor lesion/lymph node as measurable or non-measurable at baseline.

12.1.1 Measurable Lesions

12.1.1.1 Tumor Lesions

Must be accurately measured in at least one dimension (longest diameter in the plane of measurement is to be recorded) with a minimum size as follows:

- 10 mm by CT scan (CT scan slice thickness no greater than 5 mm; see Appendix II of Eisenhauer et al, 2009 for imaging guidance)
- 10 mm caliper measurement by clinical exam (lesions which cannot be accurately measured with caliper should be recorded as non-measurable)
- 20 mm by chest X-ray

12.1.1.2 Malignant Lymph Nodes

To be considered pathologically enlarged and measurable, a lymph node must be ≥ 15 mm in short axis when assessed by CT scan (CT scan slice thickness recommended to be no greater than 5 mm). At baseline and in follow-up, only the short axis will be measured and followed. For additional information on lymph node measurement, see notes in Eisenhauer et al, 2009 under the heading “Baseline documentation of target and non-target lesions,” as well as a companion paper on lymph node assessment using RECIST⁵⁰.

12.1.2 Non-measurable Lesions

Non-measurable lesions are all other lesions, including small lesions (longest diameter < 10 mm or pathological lymph nodes with ≥ 10 to < 15 mm short axis) as well as truly non-measurable lesions. Truly non-measurable lesions include leptomeningeal disease, ascites, pleural or pericardial effusions, inflammatory breast disease, lymphangitic involvement of skin or lung, and abdominal masses/abdominal organomegaly identified by physical exam that is not measurable by reproducible imaging techniques.

12.1.3 Special Considerations Regarding Lesion Measurability

Bone lesions, cystic lesions, and lesions previously treated with local therapy require particular comment.

12.1.3.1 Bone Lesions

Bone scan, PET scan, or plain films are not considered adequate imaging techniques to measure bone lesions. However, these techniques can be used to confirm the presence or disappearance of bone lesions.

Lytic bone lesions or mixed lytic-blastic lesions, *with identifiable soft tissue components*, that can be evaluated by cross-sectional imaging techniques such as CT or MRI can be considered as measurable lesions if the soft tissue component meets the definition of measurability described above.

Blastic bone lesions are non-measurable.

12.1.3.2 Cystic Lesions

Lesions that meet the criteria for radiographically defined simple cysts should not be considered as malignant lesions (i.e., neither measurable nor non-measurable) since they are, by definition, simple cysts.

Cystic lesions thought to represent cystic metastases can be considered as measurable lesions if they meet the definition of measurability described above. However, if non-cystic lesions are present in the same individual, these are preferred for selection as target lesions.

12.1.3.3 Lesions with Prior Local Treatment

Tumor lesions situated in a previously irradiated area, or in an area subjected to other loco-regional therapy, are usually not considered measurable unless there has been demonstrated progression in the lesion.

12.1.4 Methods of Tumor Measurement

Please refer to Eisenhauer et al, 2009, Section 3.2 for details concerning details of how measurements of lesions/lymph nodes should be done. For the current study, CT is the only acceptable measurement method.

12.2 Tumor Response Evaluation

12.2.1 Designation of Target and Non-Target Lesions

When more than one measurable lesion is present at baseline, all lesions, up to a maximum of 5 lesions (and a maximum of 2 lesions per involved organ) representative of all involved organs should be identified as target lesions and will be recorded and measured at baseline. In the current study, the baseline measurement will be based on the scans and measurements taken at the end of the pre-study standard chemotherapy, as submitted by the investigator.

Target lesions should be selected on the basis of their size (lesions with longest diameter) and be representative of all involved organs, but in addition should be those that lend themselves to reproducible repeated measurements. It may be the case that on occasion, the largest lesion does not lend itself to reproducible measurement; in such cases, the next largest lesion that can be reproducibly measured should be selected.

A sum of the diameters (longest for non-nodal lesions, short axis for nodal lesions) for all target lesions will be calculated and reported as the baseline sum diameters. The baseline sum diameters will be used as the reference to characterize any objective changes in the measurable dimension of disease.

All other lesions or sites of disease (i.e., non-measurable lesions), including pathological lymph nodes, should be identified as non-target lesions. Measurements of non-target lesions, even if measurable, are not required, as they are intended to be assessed qualitatively and should be designated as present or absent at baseline. It is also possible to record multiple non-target lesions in the same organ as a single item, e.g., "multiple enlarged pelvic lymph nodes."

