1.0 PROTOCOL SUMMARY AND/OR SCHEMA

This is an open-label, single institution, phase Ib/phase II non-randomized trial that evaluates the safety, tolerability and anti-tumor activity of fulvestrant and Debio 1347 in patients with ER+/HER2- metastatic breast cancer (MBC) that are FGFR-amplified (as confirmed by a CLIA certified laboratory). The phase Ib portion will evaluate 2 dose cohorts (80mg (cohort/dose level 1), and one dose de-escalation cohort (60 mg dose level -1) in case dose level 1 is deemed to have intolerable toxicity. Only the dose of Debio 1347 will be de-escalated. Fulvestrant will be administered intramuscularly at standard doses. Total number of patients expected in the phase 1b portion: minimum 4 and maximum 12.

The phase 2 portion will be comprised of an optimal Simon two-stage design to determine the efficacy (defined as clinical benefit rate (CBR): overall response rate (ORR) + Stable disease (SD) \geq 24 weeks) of Debio 1347 plus fulvestrant. Patients enrolled to the phase II portion will be treated at the recommended phase 2 doses (RP2D) identified from the phase Ib portion of the study. Total number of patients expected in the phase 2 portion: minimum 18, maximum 43.

Briefly, patient's eligibility criteria will include: pre/peri/post-menopausal women and men with metastatic ER+/HER2-/FGFR-amplified breast cancer, in first or second line of treatment in the metastatic setting (phase II portion) without prior use of a FGFR inhibitor; ECOG performance status ≤ 1 , normal baseline blood counts and chemistry laboratory profile; and no intercurrent uncontrolled illness. Treatment will be given until disease progression or unacceptable toxicity. To assess the anti-tumor effect of therapy, we will estimate the overall tumor burden at baseline to which subsequent measurements (performed every 8 weeks for the first 6 months and then every 12 weeks thereafter using the Solid Tumor Response Criteria [RECIST] v1.1) will be compared.

Pharmacokinetic and pharmacodynamic data will be obtained throughout the phase Ib/Phase II portion of the study. A baseline biopsy of a metastatic site will be required for all the patients enrolled on the trial, with the acquisition of at least 3 fragments of a core biopsy and in addition archival tissue will also be obtained, whenever available. Tissue will be evaluated for FGFR amplifications by FISH and protein and mRNA expression in collaboration with [name].

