6.1 CRITERIA FOR SUBJECT ELIGIBILITY

6.2 Subject Inclusion Criteria

- Males and Females, Age > 18 years
- Written informed consent and authorization obtained from the subject/HIPAA-appointed legal representative prior to performing any protocol-related procedures including screening evaluations.
- Patients with metastatic histologically or cytologically confirmed invasive breast cancer.
- Female patients of postmenopausal status
Postmenopausal status will be defined as following:
 - Age \geq 60 years
 - Age < 60 years and 12 months of amenorrhea plus follicle stimulating hormone and plasma estradiol levels within postmenopausal range by local laboratory assessment in the absence of oral contraceptive pills, hormone replacement therapy, or gonadotropin-releasing hormone (GnRH) agonist or antagonist
 - Prior bilateral oophorectomy
- Pre or perimenopausal women allowed with the addition of goserelin.
- ECOG performance status 0 -1
- Tumor must be estrogen receptor and/or progesterone receptor positive (i.e. Hormone receptor positive (HR+) and HER-2 negative as defined by the ASCO-CAP guidelines: HR+ is defined as expression of ER and/PR in \geq 1% of cells, or HR+ by local laboratory or regional definition. HER2- is defined as a HER2 IHC score of 0 or 1+, or an IHC score of 2+ accompanied by a negative fluorescence, chromogenic, or silver in situ hybridization test indicating the absence of HER2 gene amplification, or a HER2/CEP17 ratio of < 2.0, or local clinical guidelines.

- Tumors must have FGFR amplifications as determined by a CLIA certified laboratory. Patients with FGFR amplifications co-occurring with 11q amplification (CCND1, FGF3,4, 19 amplifications) are also eligible.
- Measurable or evaluable disease per RECIST1.1 or pure lytic or mixed lytic-blastic bone lesions
- No more than 1 prior chemotherapy regimen in the metastatic setting for the phase 2 portion. Patients in the phase 1 portion could have received any number of prior lines of therapy.
- Willing to undergo a new core or excisional biopsy from a metastatic, not previously irradiated tumor lesion during screening
- Life expectancy of greater than 3 months
- Archival Tumor (up to 10 unstained slides) will be obtained, whenever available for additional biomarker analyses
- Hematologic parameters:
 - White blood cell (WBC) count of > 3000/ μ l
 - Absolute neutrophil count (ANC) > 1000/ μ l
 - Platelets > 100,000/ μ l, hemoglobin > 9.0 g/dl
- Non-hematologic parameters:

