- Known untreated or uncontrolled acute infection, including urinary tract infection, within 7 days of study entry.
- History of organ, bone marrow, or stem cell transplantation.
- Pregnant or lactating woman (any woman of childbearing potential who has menstruated within the year prior to enrolment will undergo pregnancy testing within 72 hours prior to receiving the first dose of study medication).
- Women of childbearing potential or men who are unwilling to use an appropriate method of contraception during the study period and for 6 months after completing treatment with Debio 1347. Oral or injectable contraceptive agents cannot be the sole method of contraception. Note: Abstinence is acceptable if this is the usual lifestyle and preferred contraception for the subject.
- Poorly controlled diabetes mellitus or hypertension (e.g., systolic > 180 mmHg or diastolic > 100 mmHg).
- Inability or unwillingness to swallow oral medications.
- Clinically significant gastrointestinal abnormality that would affect the absorption of drug such as gastrointestinal dysfunction, malabsorption syndrome, major resection of the small bowel or total gastrectomy or inflammatory bowel disease.
- Uncontrolled hydropericardium.
- Chemotherapy or radiotherapy within 14 days prior to starting study treatment. In case of monoclonal antibodies/biologics, within 28 days prior to starting study treatment.
- Administration of investigational agents within 28 days prior to treatment initiation.
- Major surgery and surgery for brain metastases within 28 days prior to screening start. Of note, Intravenous port placement is not considered as a major surgery.

- Not recovered from AEs or toxicities due to previous treatments to a Grade 1 or less specified in NCI-CTCAE version 4.0 excepting, albumin (< 2.5 g/dL), AST and ALT in patients with liver metastases ($> 5 \times$ ULN) ALP in patients with bone metastases ($> 5 \times$ ULN) and alopecia.
- Prior use of a drug targeting FGF or FGFR. Patients previously treated with medications that affect FGFR signaling as a secondary target (e.g., multi-tyrosine kinase inhibitors that primarily inhibit VEGF, but to a lesser extent also affect FGFR signaling) can be considered after discussion with the Principal Investigator.
- Currently under alcohol or drug abuse rehabilitation or treatment program.
- Uncontrolled intercurrent illness or psychiatric illness/social situations that would limit compliance with study requirements.

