Eligibility Note: Patients could have progressed on prior aromatase inhibitors

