8.1 PRETREATMENT EVALUATION

To be completed within 28 days of starting Cycle 1 Day1 (unless otherwise indicated):

- Signed informed consent for study participation
- History and physical examination including height, weight, vital signs (temperature, pulse rate, respiratory rate, blood pressure, pulse oximetry), performance status (ECOG), and review of pathology and concomitant medications: medications taken within 28 days of starting Debio 1347 and fulvestrant
- Urine or serum pregnancy test for all women of childbearing potential. If the test result is positive related to pregnancy, the patient will not be allowed to participate in this study
- CBC with differential and platelet count
- Complete metabolic panel (sodium, potassium, chloride, bicarbonate, BUN, creatinine, glucose, total protein, albumin, bilirubin, alkaline phosphatase, AST, ALT, calcium)
- Magnesium

- Phosphorous
- γ GTP
- CPK
- CRP
- Uric Acid
- LDH
- Calcium regulating hormones (whole-PTH, 1,25(OH)2D, PTHrP)
- PT/INR & aPTT
- Serology for HepBsAg, HepBcAb, HIV and hepatitis C antibody (negative test acceptable prior to screening period)
- Tumor markers: CEA and Ca 15-3
- Urinalysis including urinary protein, blood, glucose, urobilinogen, pH, sediment, creatinine, calcium (CA), phosphate
- 12-lead Electrocardiogram (EKG)
- ECHO
- Complete ophthalmologic examination. The examination will be interpreted by a qualified ophthalmologist, including visual acuity testing, slit-lamp ophthalmoscopy and indirect ophthalmoscopy.
- CT scan with contrast (chest, abdomen and pelvis). If patient is unable to receive CT contrast, or the abdominal/pelvic target lesion is indeterminate on CT scan, then MRI with contrast (abdomen and pelvis) plus CT chest without contrast may be performed.
- A baseline brain MRI or CT scan with contrast (the same method of imaging done at baseline should be done throughout the study at indicated time points) is required only for patients with a history of brain metastases
- Research blood samples: for PK and cfDNA as detailed in section 12.0
- Baseline tumor biopsies will be obtained during screening for all patients enrolled in the study

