10.1 EVALUATION DURING TREATMENT/INTERVENTION

	Screening	Treatment							EOT	F/U ^a
Cycle		1				2		3+		Every 12 weeks
Day	-28 to -1	1	4	8	15	28	1	15	1	
		±2	±1	±2	±2	-4	±3	±3	±3	±7
										±14
Written Informed Consent	X									
Review of Eligibility Criteria	X									
Demographic Information	X									
Vital Signs, ECOG PS ^b	X	X			X		X	X	X	X
Height	X									
Physical Exam and Weight	X	X			X		X	X	X	X
12-lead ECG ^c	X	X				X			X	X
ECHO ^c	X								X	X
Haematology and Chemistry blood work ^d	X	X		X	X		X	X	X	X
Tumor markers (CEA and CA15-3)	X	X					X		X	X
Other Bloodwork (CRP LDH, uric acid and γGTP)	X	X		X	X		X	X	X	X
Phosphate (P)			X							
Blood coagulation (PT (INR), APTT)	X	X					X		X	X
Urinalysis ^e	X	X		X	X		X	X	X	X
Calcium regulating hormones bloodwork ^f	X	X					X		X	X
Serum pregnancy test	X									X
Ophthalmological testing ^g	X									X
Adverse events		X		X	X	X	X	X	X	

Fulvestrant		X			X	X			X		
Tumour assessment^h	X								X	X	
Plasma sample for CfDNAⁱ		X			X				X	X	
Pharmacokinetics^j		X			X		X		X		
Tumor Biopsy^k	X										
HepBsAg, HepBcAb, HIV and hepatitis C antibody^l	X										

Abbreviations: DEXA, dual-energy X-ray absorptiometry; ECHO, echocardiogram; ECOG, Eastern Cooperative Oncology Group; EOS, end-of-study; EOT, end-of-treatment (any study treatment); IV, intravenous; PS, performance status.

- a) Survival and disease status will be assessed every 12 weeks (+/- 14 days) until death, withdrawal of consent, or end of the study, whichever is first. Assessments can be collected through phone call or review of patient records.
- b) Blood pressure and heart rate to be collected. BP and pulse rate to be taken after at least 5 minutes of supine rest.
- c) ECG recorded every 3RD cycle *after* Cycle 3. If an ECG shows QTc prolongation (> 470 msec.), the ECG must be repeated twice additionally to obtain values in triplicate. ECHO will be done at baseline, every 3 cycles and at EOT during the phase 1 portion of the study.
- d) Haematology: red blood cells, haemoglobin, hematocrit, platelet count, white blood cells, neutrophils, lymphocytes, monocytes, eosinophils, basophils.
- Blood chemistry(Fasting): total protein, albumin, total bilirubin, AST, ALT, LDH, ALP, γ GTP, CK, total cholesterol, sodium (Na), potassium (K), calcium (Ca), chloride (Cl), phosphate (P), magnesium (Mg), creatinine, BUN, CRP, uric acid, glucose.
- e) Urinalysis: protein, blood, glucose, urobilinogen, pH, sediment, creatinine, calcium (Ca), phosphate (P).

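### Section 12.2.1 takes the RECIST baseline from an end-of-chemotherapy scan, sections 8.1 and 10.1 require a screening scan, and nothing says which governs; where the two differ, pre-study change enters the primary endpoint

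*Combined protocol and SAP*

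**What the plan says.** Section 12.2.1 gives a rule specific to this study: "the baseline measurement will be based on the scans and measurements taken at the end of the pre-study standard chemotherapy". The same section makes the resulting sum of diameters the reference for later change.

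Other sections point to a different scan. Section 8.1 lists CT of chest, abdomen and pelvis among the pretreatment evaluations, headed "To be completed within 28 days of starting Cycle 1 Day1 (unless otherwise indicated". In the section 10.1 table the row "Tumour assessment^h" is marked in the screening column, days -28 to -1. Section 1.0 says only that "we will estimate the overall tumor burden at baseline to which subsequent measurements" will be compared, without naming the scan.

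On prior treatment, section 1.0 describes phase II patients as "in first or second line of treatment in the metastatic setting (phase II portion", and section 6.2 sets a ceiling but no minimum: "No more than 1 prior chemotherapy regimen in the metastatic setting for the phase 2 portion". Section 6.3 excludes "Chemotherapy or radiotherapy within 14 days prior to starting study treatment", and its eligibility note adds that "Patients could have progressed on prior aromatase inhibitors". Section 14.0 states that prior palbociclib is allowed.

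In Table 2 (section 12.2.2.1), PR is a fall of at least 30% from the baseline sum. PD is a rise of at least 20%, and at least 5 mm, over the lowest sum during the study, with baseline counted if it is the lowest. Section 14.0 builds the primary endpoint, CBR, from CR, PR and SD lasting at least 24 weeks.

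**The concern.** The response reference should be the tumour burden at the start of treatment. Section 12.2.1 places it at the end of an earlier treatment that the eligibility criteria do not require. This raises three problems.

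- **No baseline for some eligible patients.** A patient with no prior chemotherapy has no scan of the kind that 12.2.1 describes. That patient does have a screening scan, so patients in one analysis could be measured against different kinds of baseline.
- **No maximum age for the scan.** Section 6.3 sets a minimum of 14 days off chemotherapy and no maximum. An aromatase inhibitor or palbociclib may have been given in between.
- **Two permissible readings.** With both rules in force, a tumour sum can be scored from either scan, and the choice is not fixed before results are seen.

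Section 14.0 decides stage 1 on 2 versus 3 patients of 18, and the trial on 7 versus 8 of 43, so a few reclassified patients could matter. ORR, TTP and PFS use the same reference.

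**Working it through.** **1. The plan's own design figures.** With X1 ~ Bin(18, p) and X2 ~ Bin(25, p), early termination at p = 0.10 has probability P(X1 <= 2) = 0.734 (stated 0.73). The probability of a positive result is the sum over x = 3 to 18 of P(X1 = x) * P(X2 >= 8 - x). This gives 0.048 at p = 0.10 (stated 5%) and 0.800 at p = 0.25 (stated 80%). The Simon design reproduces and is not in question.

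**2. The two baselines side by side.**

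| | Section 12.2.1 | Sections 8.1 and 10.1 |
|---|---|---|
| Scan | End of pre-study chemotherapy | Screening assessment |
| Window before Cycle 1 Day 1 | None stated | 28 days |
| Exists for every eligible patient | No, prior chemotherapy is optional | Yes |

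The scans can coincide: a 14-day minimum off chemotherapy fits inside a 28-day window. Nothing requires it.

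**3. Effect on PR (measurable disease only).** Let B be the end-of-chemotherapy sum, S the screening sum and r = S/B. The documents give no distribution for r, so the values are assumed. PR needs a sum of at most 0.70B = (0.70/r)S, a fall from screening of 1 - 0.70/r.

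| r | Fall from screening needed for PR |
|---|---|
| 0.8 | 1 - 0.875 = 12.5% |
| 0.9 | 1 - 0.778 = 22.2% |
| 1.0 | 30.0% |
| 1.1 | 1 - 0.636 = 36.4% |
| 1.2 | 1 - 0.583 = 41.7% |

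At r = 0.7 the required fall is 0%, so a tumour unchanged on study is a PR.

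**4. Effect on PD at the first on-treatment scan, r of 1 or more.** B is then the lowest sum before that scan, so the threshold is 1.20B = (1.20/r)S, a change from screening of 1.20/r - 1. This is +20.0% at r = 1.0, +9.1% at r = 1.1 and 0% at r = 1.2. The 5 mm rule applies as well. Confirmation at least 4 weeks later does not remove the effect, because it uses the same reference.

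**5. Examples in mm (assumed: end of chemotherapy, screening, on study).**

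- 50, 60, 60: +20% and +10 mm from 12.2.1's baseline, so PD if confirmed; 0% from screening, so SD.
- 50, 60, 42: (42 - 50)/50 = -16%, SD; (42 - 60)/60 = -30%, PR.
- 80, 55, 55: (55 - 80)/80 = -31%, PR; 0% from screening, SD.

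**6. Route into CBR.** As section 14.0 is written, a PR counts without the 24-week condition, so a PR created by shrinkage before entry adds a benefit. Early PD created by growth before entry removes one. A PR downgraded to SD always changes ORR, but changes CBR only if the SD falls short of 24 weeks.

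**7. Timing used for the lesser points.** Elapsed days from Cycle 1 Day 1 = (cycle - 1) * 28 + day - 1. Cycle 6, days 22 to 28, gives 161 to 167; 24 weeks is 168.

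**The case against.** The strongest reply is that the sentence is a leftover and that staff would naturally use the screening scan. There is support for this. Sections 12.2.2.2, 12.2.2.4.1 and 12.2.2.5 cite Tables 17, 18 and 19, although the protocol's tables are numbered 1 to 4, so the response section looks carried over from another document. If the screening scan is used in practice, no patient is misclassified. That limits the likely harm but leaves the rule wrong, because 12.2.1 is worded as applying to this study and nothing overrides it.

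Four stronger readings are tempting, and the documents do not support them.

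- **That pre-study change is scored in the primary endpoint for everyone.** The two scans may be the same scan. The sums also do not apply to patients with only non-measurable disease, whom sections 6.2 and 12.3.3 admit.
- **That type I error rises or power falls by a stated amount.** Any such figure needs misclassification rates, and none is given. The direction is also undetermined: growth before entry makes PR harder and PD easier, while shrinkage makes PR easier.
- **That for r below 1 the PD threshold rises in step, for example to +50% at r = 0.8.** Table 2 uses the lowest sum during the study. If the screening sum counts as such, the threshold stays at +20% from screening. No PD figure is claimed for r below 1.
- **That SD still present at cycle 8 or 9 meets 24 weeks however it is timed.** If SD is timed from the first scan showing it, cycle 2 day 28 (55) to cycle 8 day 22 (217) is 162 days. Cycle 3 day 28 (83) to cycle 9 day 22 (245) is also 162 days. Both are under 168.

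**Conclusion.** The point stands as an unreconciled contradiction over the reference scan for the primary endpoint, and it should be corrected before responses are scored. Section 12.2.1 gives no baseline for an eligible patient without prior chemotherapy and an undated one for the rest.

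The size is conditional. For measurable disease and an assumed r, the fall from screening needed for PR runs from 12.5% (r = 0.8) to 41.7% (r = 1.2). At r = 1.2 an unchanged tumour reaches the PD threshold at the first scan, subject to the 5 mm rule and confirmation. How often the scans differ, and the net effect on CBR, cannot be derived from the documents. Sample size and stopping rules are unaffected.

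Three related points are separate and lesser.

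- **Scan schedule.** Section 1.0 agrees with the cycles listed in footnote h of section 10.1 (2, 4, 6, then 9, 12, 15). The outliers are the 48 weeks in that footnote and the 3-cycle interval in 12.2.2.4.1.
- **SD duration.** The protocol body gives no origin or tolerance. Counted as elapsed days from Cycle 1 Day 1, the cycle 6 window ends 1 to 7 days short of 24 weeks; another origin could remove the shortfall. The RECIST article in Appendix B was not available to check.
- **PD confirmation.** Table 2 asks for it generally; 12.2.2.4.1 asks for it only at the first response scan.

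**What to change.** Delete the end-of-chemotherapy sentence from 12.2.1. Define baseline, for every patient, as the last tumour assessment in the day -28 to -1 screening window before Cycle 1 Day 1. Reconcile the MRI option in 8.1 with 12.1.4, which accepts CT alone for measurement.

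This is a wording change. It needs no new scan, because the screening assessment is already required, and it leaves the Simon design as it is. Section 9.2.1 shows that the trial was under way at this amendment, with all phase 1 patients off study. Any enrolled patient already scored from an older scan would therefore need re-scoring from the existing screening scan.

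Separately:

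- Bring the 48-week figure in footnote h and the 3-cycle interval in 12.2.2.4.1 into line with section 1.0 and the listed cycles.
- State in section 14.0 the origin and tolerance for the 24-week SD criterion. If the origin is Cycle 1 Day 1, a 7-day tolerance covers the cycle 6 window without another scan, at the price of accepting SD up to 7 days short.
- Use one PD-confirmation rule in Table 2 and 12.2.2.4.1, and say how unconfirmed PD counts toward CBR.
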